Research objectives	
Primary Objective: To evaluate the effectiveness of reactive case detection (RACD) using HS-RDTs, targeting both village and forest working populations, compared to control for reducing the health center catchment-level incidence and prevalence of P. falciparum and P. vivax within two provinces in Lao PDR.
 
Secondary Objectives:
 
 1. To determine the operational feasibility, cost-effectiveness, and acceptability of targeting high-risk populations with community-based reactive case detection strategies aimed at reducing P. falciparum and P. vivax transmission among village and forest working populations. 2. To determine the operational feasibility and safety of conducting G6PD testing and PQ administration and follow-up at the community level. 3. To determine factors associated with G6PD testing after referral to district or provincial-level facilities for persons with P. vivax positive RDT results, and subsequent adherence to Primaquine treatment. 4. To assess malaria vector species composition and bionomics in both village and forest settings
Study site and target populations	Total population of approximately 120,000 in 32 health center catchment areas of two Provinces in Lao PDR (Champasak and Saravan Province)
Study design	A cluster randomized controlled trial design will be used to evaluate the enhanced RACD intervention against standard of care
Primary outcome measures for assessing impact	
 1. Cumulative incidence over the study period at the health facility level 2. Prevalence of infection (P. falciparum and/or P. vivax) using qPCR 3. HS-RDT and RDT test positivity rate for RACD
Data collection and sampling period	18 months from start date (June 2019 – November 2020)

Sample size	32 health center catchment areas in Lao PDR

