2.5. Study overview

To test this hypothesis, this study will employ a cluster randomized controlled trial design with two comparison arms:

1. **Control:** standard of care - passive case management provided through community-based VMWs and existing health facilities; includes village-based RACD with conventional RDTs conducted by district surveillance teams.
2. **Enhanced community-based RACD:** RACD conducted by community-based VMWs using both HS-RDTs and conventional RDTs within villages and among forest workers.

The primary outcome measures to assess effectiveness include *P. falciparum* and *P. vivax* confirmed case incidence over the study period; PCR-based *P. falciparum* and *P. vivax* prevalence at endline; and HS-RDT test positivity rate in village and forest worker RACD. Secondary outcomes measures will examine the operational feasibility, safety, and acceptability of VMW-led reactive approaches and G6PD testing, referral to district or provincial-level facilities, safety and treatment adherence for *P. vivax* cases. The trial will be implemented between June 2019 and December 2020 in Lao PDR. The primary evaluation will be conducted following an end-line cross-sectional survey in November/December 2020.

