3.4. Study evaluation methods

3.4.1. Overview of evaluation activities by study objectives, outcomes, and data collection activities

Table 4. Overview of evaluation activities

Study activity	Research objective	Primary outcome measures	Data collection activity
Activity 1: Impact evaluation of enhanced RACD	1. Evaluate the relative effectiveness of enhanced community-based RACD using HS-	Total confirmed outpatient (OPD) P. falciparum and P. vivax malaria case incidence among all ages by health facility catchment	Routine malaria data from all reporting VMWs, health centers and district hospitals

	RDTs in villages and forest-based HRPs, compared to control	P. falciparum and P. vivax prevalence in all individuals	Cross-sectional parasite survey November-December 2020	
		HS-RDT and RDT test positivity rate	HS-RDT and RDT positivity data from RACD intervention data	
Activity 2: Assessment of the feasibility and acceptability of community-based RACD	1. Assess the operational feasibility of community-based RACD	Population coverage of RACD and interventions	RACD intervention data	
		Proportion of VMWs who rate conducting the RACD interventions as very easy, somewhat easy, somewhat difficult, and very difficult, and changes in proportions over time	Entrance, mid-intervention, and exit competency checklists with VMWs; focus group discussion and interviews with VMWs at end-line	
		Costs of RACD as unit and total costs; cost-effectiveness will be assessed as an incremental cost effectiveness ratio (ICER)	Program data on costs combined with estimates of program effectiveness	
	2. Assess the acceptability of community-based RACD	Proportion of targeted individuals refusing RACD intervention	RACD intervention data	
		Proportion of survey respondents who strongly disagree, disagree, are ambivalent, agree and strongly agree on the importance and acceptability of community-based RACD	Cross-sectional survey and qualitative studies at endline with villagers, forest workers, VMWs and other health sector staff	

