The HS-RDT and RDT test positivity rate will be estimated for the RACD areas during each intervention. This will be done as soon as data on HS-RDT results are available. Differences in test positivity measures over time and between village and forest base samples will be assessed using a χ^2 test, as well as logistic regression models to account for potential confounding factors.

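### RACD test positivity (Outcome 3) gets a chi-square test that ignores grouping of contacts by index case, and is called a primary effectiveness outcome without a control-arm comparison

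*Protocol*

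**What the plan says.** **Analysis.** Protocol section 3.4.2.6, Outcome 3, restricts estimation to the intervention side: "The HS-RDT and RDT test positivity rate will be estimated for the RACD areas during each intervention". The contrasts and the test follow: "Differences in test positivity measures over time and between village and forest base samples will be assessed using a" chi-square test, "as well as logistic regression models to account for potential confounding factors". Neither method is given a clustering term. In the same section, Outcomes 1 and 2 each have random intercepts at health center catchment (HCCA) level.

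**Grouping of the data.** Section 3.4.2.4.3 expects 720 index cases, 5 households per response, 4 people per household and 4 forest workers per case. Section 3.4.2.5.3 links each contact to the index case by a code and names clustering by index case as one adjustment this permits.

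**Status of the outcome.** The Protocol summary (section 1) lists "HS-RDT and RDT test positivity rate for RACD" among the primary measures of impact. Section 2.5 says "The primary outcome measures to assess effectiveness include" three items, the last being "HS-RDT test positivity rate in village and forest worker RACD". Section 3.4.2.3 lists it as primary outcome 3, and section 3.4.2.6 analyses it under a heading for primary outcomes. The overview table in section 3.4.1 places it under an objective that ends "RDTs in villages and forest-based HRPs, compared to control", with the data source given as "HS-RDT and RDT positivity data from RACD intervention data".

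**The concern.** A chi-square test treats every tested person as independent. Household members and near neighbours of one malaria case share exposure, and so do co-workers from one forest site, so their results may be correlated. Adjusting for confounders does not correct the variance for this. Followed as written, the over-time comparison could report a trend in positivity with a p-value that is too small.

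The label is a second and separate issue. A reader of sections 1, 2.5 and 3.4.2.3 expects each primary effectiveness outcome to say something about enhanced RACD against standard of care. Outcome 3 has no control-arm data and no arm contrast, so a change over time within the intervention arm could be presented as a primary effectiveness result without bearing on the null hypothesis.

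**Working it through.** **1. The plan's own figure.** Section 3.4.2.4.3: 720 × 5 × 4 = 14,400 villagers; 720 × 4 = 2,880 forest workers; sum 17,280. This reproduces the stated total and the two components in the Protocol summary. Group size per index case is m = 20 (village) or m = 4 (forest).

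**2. Inputs not in the documents (assumptions).** ICC within an index event: 0.01, 0.05, 0.10. Test level: 5%, two-sided. Periods: two, with events split equally. f: the share of the ICC that is a stable difference between the 16 intervention catchments.

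**3. Over-time contrast.** With equally many events per catchment in each period, the stable catchment part cancels, leaving

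DEFF = 1 + (m − 1 − m·f) × ICC, and true error = 2 × [1 − Φ(1.96/√DEFF)].

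The result does not depend on the number of events.

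| Sample | f | ICC 0.01 | ICC 0.05 | ICC 0.10 |
|---|---|---|---|---|
| Village, m = 20 | 0 | DEFF 1.19, 7.2% | 1.95, 16.0% | 2.90, 25.0% |
| Village, m = 20 | 0.5 | 1.09, 6.0% | 1.45, 10.4% | 1.90, 15.5% |
| Village, m = 20 | 0.9 | 1.01, 5.1% | 1.05, 5.6% | 1.10, 6.2% |
| Forest, m = 4 | 0 | 1.03, 5.3% | 1.15, 6.8% | 1.30, 8.6% |

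Example: m = 20, f = 0, ICC 0.05 gives DEFF = 1 + 19 × 0.05 = 1.95; 1.96/√1.95 = 1.404; error 16.0%.

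The f = 0.9 row needs an equal catchment mix. When the mix varies at random between periods, cancellation is only partial. A beta-binomial simulation of the village test (240 or 720 events, positivity 0.2 to 2%, all assumed except the 720) gives, at f = 0.9, about 6–8%, 7–15% and 9–21% for the three ICCs.

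**4. Village versus forest.** Let r be the correlation between the village and forest effects of the same index case. If every case triggered both samples, the ratio of true to assumed variance would be

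[(1 + 19·ICC)/14,400 + (1 + 3·ICC)/2,880 − 2r·ICC/720] ÷ [1/14,400 + 1/2,880].

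At ICC 0.05: r = 0 gives 1.283 (error 8.4%); r = 1 gives 0.95 (error 4.4%). At ICC 0.10: 1.567 (11.7%) and 0.90 (3.9%). The sign depends on r, which is unknown. Under section 3.3 only forest-exposed cases trigger both samples, so the overlap is unknown too.

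**5. Status of the outcome, set side by side.**

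- Called primary for impact or effectiveness: sections 1, 2.5, 3.4.2.3 and the heading in 3.4.2.6.
- Data: intervention RACD only (3.4.1, 3.4.2.6). Control-arm RACD is village-based, uses conventional RDTs and is run by district teams (2.5), in some areas only (Table 5). No like-for-like contrast could be built later.
- Hypotheses in sections 1 and 2.4: incidence and prevalence only.
- Sample size (3.4.2.4.3): positivity is to be monitored, with no formal calculation.

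The protocol's own use of the measure is as yield, which does not match its label.

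**6. Sparsity.** The only positivity figure for contacts in the documents is 0.2%, by PCR in another setting (section 2). If it applied here, 14,400 × 0.002 ≈ 29 positives among villagers over 720 events.

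**The case against.** **Clustering detail belongs in the SAP.** Section 3.4.2.5.3 records the intention, section 3.4.2.6 also names logistic regression, and the protocol nowhere calls its chi-square test unadjusted. A reader might infer that the protocol overlooked clustering; it did not. What stands is narrower: section 3.4.2.6 names a specific test that does not suit data collected in groups, and gives its regression another purpose.

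**The size is unanchored.** This is correct. ICC, f, the split and the level are all assumed, and the range includes almost no inflation. A reader might also infer that every Outcome 3 p-value will be too small. The documents do not support that: forest samples are affected much less, and village versus forest could err in either direction.

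**The label misleads little.** The hypotheses name only incidence and prevalence, and the summary's statistical plan gives models relative to control only for those two. The protocol's background section also speaks of RACD's effectiveness in finding infections, and village against forest yield bears on the value of targeting forest workers. In the section 3.4.1 table, the reference to control belongs to the objective and not to this outcome, so that table is weaker evidence than sections 1, 2.5 and 3.4.2.3. All this supports calling positivity a yield measure. It does not support keeping it as a primary effectiveness outcome.

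**Conclusion.** The point holds in two limited parts.

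- **Test.** As written, the over-time comparison is anti-conservative if positivity correlates within index events beyond a stable catchment difference. It could be materially so for village samples and modestly so for forest samples. The size rests wholly on assumed ICCs. Near-nominal error requires both that the correlation is mostly a stable catchment difference and that the catchment mix is equal across periods.
- **Label.** Outcome 3 cannot test enhanced RACD against standard of care and should not be a primary effectiveness outcome.

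A reader might infer that the trial's main conclusion is compromised. It is not: the between-arm analyses of incidence and prevalence do not use these data and state their own catchment-level random intercepts. The change should be made because the protocol fixes both the test and the label, and the codes needed for a better analysis are already being collected.

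**What to change.** 1. In section 3.4.2.6, Outcome 3, replace the plain chi-square test with logistic regression that accounts for clustering by index event within HCCA. GEE or cluster-robust errors at HCCA level, with a small-sample correction for 16 HCCAs, are preferable. They also cover village and forest contacts of the same index case within an HCCA, whereas random intercepts at both levels may be unstable if positives are as few as the 29 above.
2. Relabel Outcome 3 as a secondary or process (yield) outcome, with no between-arm effectiveness claim, in sections 1, 2.5, 3.4.1 and 3.4.2.3 and under the heading in 3.4.2.6. Carry the change into the registry entry foreseen in section 5.4. Incidence and prevalence remain the primary between-arm outcomes.

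The cost is one fewer primary outcome, a possible registry update and slightly wider intervals for positivity. No new data are needed, because section 3.4.2.5.3 already provides the index-case codes.

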3.4.2.7. Laboratory analysis

The laboratory procedures described below will be followed for all laboratory-based activities conducted during this project. The laboratories performing these tests include the Pasteur Institutes in Phnom Penh and Paris, and UCSF.

Rapid diagnostics tests

Standard combination RDT, HS-RDTs and G6PD Carestart RDT will be used during field activities. Standard combination RDT and HS-RDTs will be used to determine malaria infection status and will be performed on participants every time a blood sample is collected. The standard combination RDT can detect *P. falciparum* and *P. vivax* malaria infection while HS-RDT can detect whether *P. falciparum* infection is present or not and is estimated to be several times more sensitive than standard RDTs; new HS-RDTs including detection of *P. vivax* will be used if they become available over the study period. The VMW will use a finger prick blood sample to run the Standard SD Bioline and HS RDTs in parallel with results available within 20 minutes and recorded by study staff. The G6PD Carestart RDT will be used by health center and hospital staff to determine the G6PD status of all individuals positive for *P. vivax* by standard RDT. All RDTs will be used according to the manufacturer's instructions. The results of these tests will be provided to the participant. For quality assurance of qualitative G6PD tests, quality assurance processes including user training, proficiency testing, and regular quality control of tests using control reagents will be introduced in intervention facilities. Images of G6PD RDTs conducted over the first three months of the study will be reviewed by laboratory technicians at the district hospital.

Filter paper sample collection

Dried blood spots (DBS) will be collected onto filter paper for future molecular analysis including parasite and human (i.e., G6PD) genotyping for research purposes only. These results will not be provided to the participants. Filter paper (Whatman 3MM) will be pre-cut into individual squares and

stapled to a thick card that will serve as its cover. Blood spots will be collected onto the filter paper in volumes of approximately 25 µl aliquots per blood spot (4 blood spots per card). Filter paper samples labelled with the individual's barcodes or ID number on the covering cardboard and will be allowed to dry at ambient temperature and relative humidity before closing the card over the filter paper. Filter paper samples will be transported from the field in a Ziploc bag then placed in a stock card filter paper box with desiccant and humidity indicator card and stored at 4°C within one week, and at -20°C within one month. Dried blood spots (DBS) will be regularly transported to the district or provincial offices for refrigerated storage prior to bulk transport and shipment to designated laboratories.

Serology

Serology, a test of past infection as assessed by the presence of antimalarial antibodies, will be used to improve the identification of hotspots and estimate current and historical transmission intensities¹⁴. Using DBS, ELISA assays will be performed using previously described methods. Briefly, antibodies will be eluted from DBS and assayed to detect antibodies against the *P. falciparum* blood stage antigens including merozoite surface protein-1 (MSP-1) and apical membrane antigen-1 (AMA-1), both biomarkers of *P. falciparum* exposure¹⁵. Markers for *P. vivax* exposure will include Pvmsp-1 and Pvcsp¹⁶. Other antigens that are sensitive and specific for recent exposure (currently undergoing evaluation) for *P. falciparum* and *P. vivax* may also be used. ELISA assays will be performed in duplicate and optical densities recorded with an ELISA reader. Other serological and antigenic platforms (bead array, protein microarray) may be used to analyze responses to multiple antigens/antibodies, if available.

Genotyping

Genotyping of *P. falciparum* infections to assess transmission networks will consist of a panel of microsatellites located throughout the genome. Briefly, DNA samples will be amplified in a multiplex pre-amplification step followed by amplification of microsatellites in individual reactions using fluorescently tagged primers and sized using denaturing capillary electrophoresis. Multilocus genotypes from mixed infections will be reconstructed, where possible, by quantifying alleles at each locus. Genotyping of additional loci including for HRP2 deletion will be performed as needed.

Individual microsatellite amplifications will be undertaken using single round or nested PCR assays with fluorescently labeled primers, and the amplicons sized by denaturing capillary electrophoresis with internal size standards. Allele-calling will be undertaken with the aid of the GeneMapper v4.0 software. The potential for effective multilocus haplotype reconstruction in polyclonal infections will be explored. Additional informative SNP markers identified in whole genome sequencing efforts may also be genotyped as necessary to improve sample fingerprinting.

Genotyping for markers of drug resistance will include PCR and/or sequencing to identify markers of resistance to artemisinin-based combination therapies (ACTs), in particular artemether-lumefantrine, artesunate-amodiaquine, dihydroartemisinin-piperaquine (including K13 and plasmepsin), and the antifolate combination sulfadoxine-pyrimethamine (SP).

Human DNA may be used in the future to screen for genetic risk factors for malaria, such as inherited blood disorders and drug metabolism e.g., G6PD variant, CYP2D6 variant. In subjects who experience an SAE and where hemolysis is suspected, G6PD genotype will be examined as well as a number of control subjects of people who were given primaquine but did not hemolyse or have an SAE. A random sample from the cross-sectional surveys may be examined for G6PD genotype in order to assess the prevalence of G6PD deficiency in study areas. No additional human genetic testing unrelated to malaria will be performed.

3.4.3. Assessment of the feasibility, acceptability, and safety

Qualitative key informant interviews (KII) and focus group discussions (FGDs) will be conducted at baseline and endline in Laos PDR.

3.4.3.1. Implementation procedures

The feasibility, acceptability and safety evaluations will be conducted using a mix of quantitative data collection and key informant (KI) interviews and focus group discussions (FGDs) of key study and health sector personnel including provincial, district, and health facility staff, VMWs, forest workers/employers and villagers/community members. In addition, participatory research methods including a process-mapping workshop at a subset of health facilities and a workshop based on the co-design of training and counselling messages for G6PD deficiency and risk factors for radical cure treatment will be conducted at baseline.

3.4.3.2. Primary outcomes measures

1. Population coverage of enhanced RACD interventions: this indicator will be measured in two ways. Operational program coverage will be defined as the proportion of individuals ≥ 18 months old and households visited and offered the RACD interventions within the target areas per time period. Effective program coverage is defined as the proportion of individuals (≥ 18 months old) that agreed to participate in the RACD intervention among all individuals ≥ 18 months old eligible to participate in the intervention in the target population per time period.
2. Feasibility of conducting enhanced RACD intervention at the community level: feasibility will be determined based upon a combination of population coverage data, responses of provincial, district, and health staff, VMWs, and community members to KIIs and FGDs at baseline and endline, VMW competency checklists at baseline, midline, and endline, and cost data.
3. Acceptability of community-based RACD approaches: acceptability will be determined based upon refusal rates during interventions and responses of community members and VMWs to endline questionnaire, interviews, and focus groups.
4. Safety of community-based RACD and treatment follow-up: safety measures will include the adverse event rate amongst treated individuals and hemoglobin measurement pre and post treatment for individuals receiving PQ.
5. Operational feasibility of G6PD referral: operational feasibility of G6PD referral will be determined by the results of the process-mapping and co-design workshops at baseline, responses of health staff and VMWs to interviews and focus groups at baseline and endline and competency checklists at baseline, midline, and endline, the proportion of referred *P. vivax* cases presenting at a health facility for G6PD testing, and the proportion of *P. vivax* cases with a valid recorded G6PD result.
6. Assessment of *P. vivax* treatment adherence: treatment adherence will be determined by the proportion of *P. vivax* cases with physical evidence of adherence through pill count, the *P. vivax* relapse rate across study arms, and the proportion of *P. vivax* cases with successful parasite clearance on day 14.

3.4.3.3. Sample size

Population coverage data for RACD interventions will be collected routinely and estimated numbers of individuals included are described in section 3.4.2.4.3 above. Focus group discussion (FGD) and key informant interview (KII) activities for feasibility and acceptability outcomes will aim to reach saturation and be comprehensive. At baseline and endline there will be a total of 1 FGD and 2 KIIs per district with provincial, district or study staff (36 KIIs total), VMWs, and recent malaria cases reporting forest travel. Supervisors will observe and complete a competency checklist on a random subset of 32 VMWs at three different time points: within the first month of intervention launch, at the midpoint of the intervention, and within the final month of the intervention. Sample sizes for quantitative (Likert

scale) acceptability data derived from cross-sectional surveys will be based on end-line sample size of 3,520 households.

